**Table 6: Adverse Events Requiring Permanent Discontinuation of Rituximab**

Severity Grade (CTCAE v4.03 Grade)	Adverse Event
Any Grade	Bowel Perforation
Grade $\geq 3$	Cardiac Arrhythmias
Any Grade	Hypersensitivity and/or Allergic Reactions to rituximab
Grade $\geq 3$	Infections
Grade $\geq 3$	Mucocutaneous Reactions
Any Grade	Progressive Multifocal Leukoencephalopathy (PML)
Grade $\geq 3$	Renal Failure
Any Grade	Viral Hepatitis

#### 5.9.2.2 Adverse Events Requiring Dose Reduction

Rituximab dose reductions are not allowed. If patients do not tolerate treatment with rituximab, they may continue on Debio 1562 alone.

For **Cohort A**, dose reduction of Debio 1562 will occur as follows:

- 0.7 mg/kg → 0.4 mg/kg

For **Cohort B**, dose reduction of Debio 1562 will occur as follows:

- 0.4 mg/kg → 0.2 mg/kg
- 0.2 mg/kg → 0.1 mg/kg

Dose of Debio 1562 should be reduced in patients experiencing the AEs below:

***Second occurrence of hematologic events:***

- Grade 4 neutropenia lasting ≥ 7 days
- Grade 3 thrombocytopenia associated with bleeding that requires transfusion
- Grade 4 thrombocytopenia lasting < 7 days
- ≥ Grade 3 febrile neutropenia

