### 5.8.2. Monitoring and Management of Cytopenias

Cytopenias (neutropenia and thrombocytopenia) have been observed in patients treated with rituximab as well as Debio 1562. In patients receiving rituximab monotherapy at  $375 \text{ mg/m}^2$  IV weekly for relapsed or refractory low-grade or follicular NHL, Grade 3-4 neutropenia occurred in 6% and grade 3-4 thrombocytopenia occurred in 2% ([Rituxan® \(rituximab\) Package Insert 2014](#)). In NHL patients who received Debio 1562 monotherapy at the dose of 0.7 mg/kg, Grade 3 neutropenia was the highest grade reported.

Patients experiencing severe cytopenia should follow the recommendations of dose-modification and additional corrective/preventive measures (such as granulocyte colony-stimulating factor [G-CSF]) present in this protocol ([Section 5.9](#)). The type of G-CSF support will be determined by the study physician, as well as the clinical judgement to decide the duration of such treatment.

If a patient develops Grade 4 thrombocytopenia lasting  $>7$  days, study treatment should be terminated and the toxicity should be followed until resolution or stabilization ([Section 5.9.2](#)).

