#### 5.9.2.1 Adverse Events Requiring Permanent Study Treatment Discontinuation

Both Debio 1562 and rituximab should be permanently discontinued in the case of the following treatment-related events:

- $\geq$  Grade 3 cardiac event
- $\geq$  Grade 3 cutaneous reactions related to rituximab treatment
- Other non-hematologic events of Grade 4 severity
- Grade 4 thrombocytopenia lasting  $>7$  days
- $\geq$  Grade 3 neuropathy
- Dose delay  $> 21$  days due to unmet retreatment criteria

Rituximab should be permanently discontinued in patients experiencing the AEs listed in [Table 6](#).

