***Other events:***

- Two dose delays (on the first day of two consecutive cycles) due to unmet retreatment criteria

Dose of Debio 1562 can be reduced for only once for a given patient, and it cannot be re-escalated. If a patient cannot tolerate treatment with Debio 1562, both Debio 1562 and rituximab should be discontinued.

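### A second Grade 4 thrombocytopenia episode lasting exactly 7 days triggers neither the dose-reduction rule (under 7 days) nor the permanent-stop rule (over 7 days)

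*Protocol*

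**What the plan says.** Three places in the Protocol set the action for Grade 4 thrombocytopenia by its duration.

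- **5.9.2.2, second occurrence of hematologic events:** Debio 1562 must be reduced for "Grade 4 thrombocytopenia lasting < 7 days".
- **5.9.2.1, permanent discontinuation:** treatment-related "Grade 4 thrombocytopenia lasting" more than 7 days stops both drugs.
- **5.8.2, cytopenias:** the same bound of more than 7 days is repeated, in which case "study treatment should be terminated and the toxicity should be followed until resolution or stabilization".

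The other items in the same second-occurrence list include "Grade 4 neutropenia lasting ≥ 7 days" and "Grade 3 thrombocytopenia associated with bleeding that requires transfusion". Under other events, 5.9.2.2 adds "Two dose delays (on the first day of two consecutive cycles) due to unmet retreatment criteria" as a trigger for reduction. It also limits reductions: "Dose of Debio 1562 can be reduced for only once for a given patient".

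Section 5.9.1 holds any dose until platelets are at least 50 x 10^9/L. If recovery takes no more than 21 days, treatment resumes at either the planned or a reduced dose, with a pointer to 5.9.2. If dosing is delayed by more than 21 days, both drugs stop.

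Section 5.9.2 defines a dose-modifying event as an adverse event that makes reduction or discontinuation necessary. SAP 10.3.1 summarises and lists those events.

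**The concern.** The rules are meant to escalate with duration: a short recurrence means a lower dose, a long episode means stopping. At exactly 7 days the required response drops to nothing and then rises to discontinuation one day later. The documents give no clinical reason for this, and elsewhere in 5.9.2.2 the boundary day is assigned: Grade 4 neutropenia includes day 7, and so does the exception for asymptomatic Grade 3 biochemistry abnormalities.

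Two things are at stake.

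- **Dosing.** After a recurrent 7-day episode the investigator may reduce the dose but is not obliged to, unless another trigger applies. Two investigators following the text could give different doses to patients with the same event.
- **Reporting.** A dose-modifying event is defined by what the protocol requires. A 7-day recurrence that requires nothing may therefore be left out of that SAP summary and listing, while a milder recurrence is included.

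**Working it through.** No sample size, power or error rate is involved. The check sets the rules side by side and then works out the dose at stake.

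**Step 1. Coverage of the duration rules.** Let d be the duration in days of a second Grade 4 thrombocytopenia episode, in a patient not yet reduced.

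| d | Reduce if d < 7 (5.9.2.2) | Stop if d > 7 (5.8.2, 5.9.2.1) | Required action |
|---|---|---|---|
| 6 | 6 < 7: yes | 6 > 7: no | Reduce |
| 7 | 7 < 7: no | 7 > 7: no | None |
| 8 | 8 < 7: no | 8 > 7: yes | Stop |

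Together the two rules cover every duration except d = 7.

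**Step 2. Could the sign have been lost in the PDF conversion?** This is unlikely. The signs for at-least and at-most survive in neighbouring items of the same section (neutropenia, febrile neutropenia, biochemistry abnormalities).

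**Step 3. Do other rules close the gap?**

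- The bleeding item names Grade 3 and needs bleeding with a transfusion. It catches only some patients.
- The consecutive-delay item and the stop after a delay of more than 21 days depend on dose delays, not on how long the episode lasted.
- The re-treatment rule in 5.9.1 delays the dose, then leaves the dose level open and refers back to 5.9.2, where the gap lies.

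Some patients with a 7-day recurrence will meet one of these triggers; others will meet none.

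**Step 4. Dose at stake, from the reduction steps in 5.9.2.2.**

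- Cohort A: "0.7 mg/kg → 0.4 mg/kg" per cycle. (0.7 - 0.4) / 0.7 = 42.9% lower.
- Cohort B, full dose: 0.4 + 0.2 + 0.2 = 0.8 mg/kg per cycle. Each dose is halved: 0.2 + 0.1 + 0.1 = 0.4 mg/kg per cycle. (0.8 - 0.4) / 0.8 = 50% lower.

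These are the protocol's ordinary reduction steps. They show what is left to discretion in an affected patient, not an average effect over the trial. The documents give no basis for estimating how often a 7-day recurrence occurs, so no rate is computed.

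**Step 5. What the outputs would still show.** Under the SAP the episode would appear in the TEAE tables and the Grade 3 or higher tables, in the grouped platelet term (10.3.1), in the platelet shift table (10.3.3.1) and, if a dose was delayed or decreased, in the exposure summary (10.4). Only the dose-modifying-event summary and listing could miss it.

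**Step 6. Coverage after the change.** With reduction at d <= 7 and stopping at d > 7, the value d = 7 falls under reduction, and each duration meets exactly one rule.

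**The case against.** The strongest reply is that the gap hardly matters. It needs a first Grade 4 episode that did not end treatment, no earlier reduction, a second episode of exactly 7 days, and none of the other triggers. Measured duration also depends on when blood is drawn: Cohort A schedules hematology only on Day 1 in Cycles 3-6, with an optional Day 15. After severe toxicity, tests are repeated within 48 hours and then at least twice weekly, so the length is only bracketed. No sensible investigator would treat 7 days as milder than 6. The investigator can reduce the dose, the investigator or sponsor can withdraw the patient for safety, and the IDMC can modify a regimen. The protocol already accepts full-dose resumption after a first episode of up to 7 days. All of this stands, and it limits the point to a minor one. It does not supply the missing rule.

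The reporting consequence is also conditional. The SAP gives no algorithm that derives dose-modifying events from episode duration, so the 7-day case may or may not be flagged. That stands, and nothing stronger is claimed.

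A further objection is that stopping at 7 days or more would close the gap equally well, would match the neutropenia convention and would be more cautious. The documents do not say which bound was intended, so this is a real alternative. It would mean altering a stop rule that is stated consistently in two sections.

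Finally, a protocol change is more than one character of work: 11.9 calls for a written amendment and possibly regulatory submissions, across approximately 55 centers.

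**Conclusion.** The concern holds. As written, a second Grade 4 thrombocytopenia episode of exactly 7 days requires neither reduction nor discontinuation, while shorter and longer recurrences each have a required action. This is a boundary slip in a stated safety rule, and it is minor.

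Its size is one duration value at a second occurrence, in patients whose dose has not already been reduced and who meet no other trigger. Frequency is unknown. Enrollment was complete by Amendment 6, so the practical reach is to patients still on treatment and to the reading of the dose-modifying-event output. The primary response endpoint and the main adverse event tables do not depend on it.

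The conclusion rests on reading the inequality signs literally and on duration being counted in whole days; the protocol gives no convention for counting them.

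**What to change.** In Protocol 5.9.2.2, change the bound for Grade 4 thrombocytopenia at second occurrence from less than 7 days to 7 days or less. Leave the stop rule of more than 7 days in 5.8.2 and 5.9.2.1 unchanged. This is the smaller edit because the stop bound appears twice. If the medical team intended to stop at 7 days, change both of those sections to 7 days or more instead.

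The text change is one inequality sign, plus the amendment handling that 11.9 requires. If no further amendment is planned, a written clarification to sites and a matching note in the derivation of dose-modifying events would serve. There is no effect on sample size or efficacy analyses.

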***Non-hematologic events:***

- Grade 3 nausea, vomiting or diarrhea, lasting more than 48 hours, despite the use of optimal supportive care
- Other non-hematologic toxicities ≥ Grade 3 except for the following:
  - AEs related to underlying disease
  - Isolated, asymptomatic Grade 3 laboratory biochemistry abnormalities that last for ≤ 7 days or have not been optimally managed

***Other events:***

- Two dose delays (on the first day of two consecutive cycles) due to unmet retreatment criteria

Dose of Debio 1562 can be reduced for only once for a given patient, and it cannot be re-escalated. If a patient cannot tolerate treatment with Debio 1562, both Debio 1562 and rituximab should be discontinued.

## **5.10. Removal of Patients from the Study**

The patient is free to withdraw consent and discontinue participation in the study at any time without prejudice to further treatment. Patients may be discontinued from study treatment, and continue to be followed per protocol, or they may be removed from the study altogether.

### **5.10.1. Discontinuation from Study Treatment**

Patients may be withdrawn from study treatment at any time at their own request, or they may be withdrawn at the discretion of the Investigator or Sponsor for safety or non-compliance to the protocol.

Reasons for permanent discontinuation of both study drugs may include the following:

- Radiological PD
- Clinical progression
- Withdrawal of consent to study treatment, but agrees to the protocol-defined follow up

- AE
- Investigator decision
- Study terminated by Sponsor
- Major protocol deviation or non-compliance
- Patient becomes pregnant
- Death
- Other

Depending on the disease state and the tumor response, patients who permanently discontinue study treatment will enter into the response and survival follow-up portion of the study: patients who had discontinued study treatment due to PD will be followed-up for survival every 12 weeks ( $\pm$  4 weeks) for up to one year from the last patient's first dose (Cycle 1 Day 1); Patients who discontinued the treatment for reasons other than PD (including treatment completion) will be followed by radiographic assessment every 12 weeks ( $\pm$  4 weeks) from the time of the patient's last on-study tumor assessment until documentation of PD or beginning of subsequent anti-cancer therapy (regimen and start date to be recorded in the EDC). After the response follow-up, patients will enter into the survival follow-up. Patients will not be required to visit the clinic for survival follow-up.

### **5.10.2. Discontinuation from the Study**

Reasons for patient discontinuation from the study are as follows:

- Withdrawal of consent to study treatment and follow up
  - If a patient withdraws from the study, and also withdraws consent for disclosure of future information, no further study-specific evaluations should be performed, and no additional data should be collected. The Sponsor may retain and continue to use any data collected before each withdrawal of consent.
- Lost to Follow-up
  - If a patient does not return for a scheduled visit, every effort should be made to contact the patient. All attempts to contact the patient and information received during contact attempts must be documented in the patient's medical record. Every effort should be made to document patient outcome.
- The study was terminated by the Sponsor
- Investigator Decision
- Death
- Other

## **5.11. Period of Observation**

For purposes of this study, the period of safety observation extends from the time the patient signs the study consent until the final safety follow-up visit.

## **5.12. Concomitant Medications and Procedures**

All concomitant medications and supportive therapy taken within four weeks before Cycle 1, Day 1 until the end of the period of safety observation must be recorded on the appropriate eCRF. The identity of all medications, dosage, and route of administration, frequency, duration of administration, and indication for use will be recorded in the appropriate sections of the eCRF.

### **5.12.1. Antineoplastic Therapy**

Other chemotherapy, investigational agents, or biologic therapy will not be permitted during the study treatment.

Palliative radiotherapy for local peripheral metastases not being used on target lesions is allowed. However, the need for such therapy may be an indication of disease progression and should be discussed with the Sponsor prior to implementation. Radiotherapy for central metastases (e.g. vertebral, mediastinal) will not be allowed; the need for such radiotherapy while on therapy will be seen as an indication of disease progression and the patient should be withdrawn from therapy.

### **5.12.2. Hematopoietic Growth Factors**

Patients receiving recombinant erythropoietin or darbepoietin alfa prior to study start may continue to receive pre-treatment doses. The use of erythropoietic growth factors may be implemented at the discretion of the treating physician or Investigator. The use of granulocyte growth factors may be implemented as specified in [Section 5.8.2](#).

### **5.12.3. Bisphosphonates**

Bisphosphonates are permitted if a patient was receiving ongoing bisphosphonate therapy at time of screening and will continue on a stable regimen throughout protocol therapy. The need to start bisphosphonates while on therapy will be seen as an indication of disease progression and the patient should be withdrawn from therapy.

### **5.12.4. Anticoagulants**

Therapeutic doses of anticoagulation therapy are permitted, as long as platelets  $\geq 100 \times 10^9/L$  ( $100,000/mm^3$ ) at baseline and the patient does not have a history of  $\geq$  Grade 2 bleeding while taking anticoagulation therapy and the patient has not been transfused within previous 10 days.

Prophylactic use of low dose anticoagulants for maintenance of line patency is also allowed.

### **5.12.5. Antivirals**

While being treated with rituximab, patients are to receive antiviral prophylaxis throughout the study per institutional guidelines. Type and dosing of such will be implemented at the discretion of the treating physician or investigator.

#### **5.12.6. Immunizations**

Vaccination with live viruses (e.g., measles, mumps, rubella, or polio) is prohibited. Vaccinations with non-live organisms (e.g., flu or tetanus) may not be effective while receiving rituximab.

#### **5.12.7. Other Concomitant Medications**

Medications for the treatment of AEs or cancer symptoms, e.g. packed red blood cells and pain medications, are allowed. Prophylactic use of steroids and/or antihistamines are required for primary prophylaxis against infusion reaction. Similarly, the use of prophylactic antibiotics are permitted if needed to mitigate risk of infection. Additional medications (not addressed above) used to treat underlying medical conditions at study entry including anti-emetics and anti-diarrheals will be allowed to continue. Antibody-maytansine conjugates with noncleavable thioether-linked DM1 as the cytotoxic agent such as Debio 1562 are not expected to have a potential for drug-drug interaction with any of the major human CYPs (see IB for additional information).

### **5.13. Overdose and Medication Error**

Overdose – There is no known treatment/antidote available for Debio 1562 or rituximab. Supportive measures should be instituted if an instance arises in which a patient suffers an overdose of study drug.

Medication Error – Any mistake made in prescribing, dispensing, administering and/or use of Debio 1562 or rituximab must be reported to the sponsor immediately and recorded on the eCRF.

## 6. PHARMACOKINETIC [REDACTED]

### 6.1. PK Assessments

Blood samples for PK measurements will be collected from all patients ([Appendix D](#), [Appendix E](#), [Appendix F](#)). Details of sample preparation and shipping are provided in the Laboratory Manual.

Debio 1562 PK – Patient plasma samples will be analyzed to measure conjugate, total antibody and/or naked antibody, free DM1 and bound DM1; additional metabolites may be evaluated.

Rituximab PK - total rituximab will be measured.

Blood samples for Debio 1562 and rituximab PK measurements in Part 1 and Part 2 of the study will be collected as described in [Appendix D](#), [Appendix E](#), [Appendix F](#).

In part 3 of the study, if the Q3W regimen is continued, the PK sampling schedule will be the same to that in the Cohort A of Part 2; if the QW regimen is continued, the PK sampling schedule will be the same to that in the Cohort B of Part 2. However, the IDMC may recommend some changes in the sampling scheme following review of trial data.

At the end of treatment (EOT) and 30-day safety follow-up visit, blood draws will be taken for PK assessment and for anti-drug antibodies (ADA).

In patients who exceptionally continue the study treatment beyond Cycle 6, the last PK sample will be taken at C7D1 at pre-dose blood draw instead of at the EOT visit. For patients already beyond C7D1 after amendment #5, the last PK sample will be taken at D1 of the next possible subsequent cycle at pre-dose blood draw instead of at the EOT visit. No additional samples will be taken at 30-day follow-up visit.

#### 6.1.1. Unscheduled Visits

Any patient who experiences a  $\geq$  Grade 2 infusion-related reaction during the administration of Debio 1562 will have blood drawn within three hours of the onset of the reaction and one week later for determination of drug concentration to Debio 1562.

PK samples may also be obtained at any time during the treatment period for assessment of treatment-related AEs, if deemed appropriate by the Investigator and Sponsor.

### 6.2. Immunogenicity Assessments

The potential immunogenicity against Debio 1562 or DM1 or rituximab will be assessed in pre-dose plasma samples at Day1 and at any time point for the other days of PK evaluation in all cycles as outlined in [Section 6.1](#), and at any time point for samples taken at the EOT and 30-day safety follow-up visit ([Appendix D](#), [Appendix E](#), and [Appendix F](#)).

In patients who exceptionally continue the study treatment beyond Cycle 6, the last sample for ADAs will be taken at C7D1 at pre-dose blood draw, instead of at the EOT visit. For patients already beyond C7D1 after amendment#5, the last ADA sample will be taken at D1 of the next possible subsequent cycle at pre-dose blood draw instead of at the EOT visit. No additional samples will be taken at the 30-day follow-up visit.

The study will evaluate the potential impact of immunogenicity on PK, safety, and anti-tumor activity of Debio 1562 and total K7153A antibody. In case of non-per protocol rituximab exposure or safety findings, the potential impact of immunogenicity on rituximab PK could be assessed.

Details of sample preparation and shipping are provided in the Laboratory Manual.

### 6.2.1. Unscheduled Visits

Any patient who experiences a  $\geq$  Grade 2 infusion-related reaction during the administration of Debio 1562 will have blood drawn within three hours of the onset of the reaction and one week later for determination of ADA formation.

## 7. TRANSLATIONAL RESEARCH STUDIES

[REDACTED]

The exploratory evaluations will be reported separately.

## **8. STUDY PROCEDURES**

The schedule of clinical [REDACTED] study assessments and procedures is detailed in the Schedules of Events ([Appendix A](#), [Appendix B](#), and [Appendix C](#)) and the schedule of PK and immunogenicity assessments are detailed in [Appendix D](#), [Appendix E](#), and [Appendix F](#).

### **8.1. Informed Consent**

Each patient must provide written informed consent before any study-required procedures are conducted, unless those procedures are performed as part of the patient's standard care.

### **8.2. Inclusion and Exclusion Criteria**

The inclusion and exclusion criteria will be assessed during screening and again on Cycle 1 Day 1 prior to dosing.

### **8.3. Confirmation of Disease Diagnosis**

At screening, disease diagnosis, the stage at original diagnosis, and current disease status will be confirmed in accordance with the Ann Arbor staging criteria ([Appendix K](#), Armitage 2005).

### **8.4. Demographic/Medical History**

The age, race, and gender of the patient are to be recorded during screening.

During the Screening period, a complete medical history for all medically relevant conditions will be compiled for each patient.

### **8.5. Prior anti-cancer treatment for Lymphoma**

All prior anti-cancer therapies for the treatment of lymphoma must be recorded in the EDC: grouping if possible the individual agents belonging to the same treatment regimen (e.g. R-CHOP, R-ICE, R-Gemox, etc), the maintenance therapy if any, with indication of the starting and end-dates, the best response achieved, and the primary reason for discontinuation if applicable. The end-date of the last treatment regimen and the date of the subsequent disease progression must be available. If applicable, the high-dose therapy and the bone marrow transplantation should be described as part of the same regimen. Reason for patients' ineligibility for HA-ASCT should be recorded as well.

